## SYNOPSIS

**Indication:** Prevention of diabetic neuropathy (DN) progression or improvement in patients with Type I diabetes (T1DM) and mild DN

**Rationale:** DN is the most common chronic complication of diabetes, ultimately affecting half of patients with T1DM and leading to severe morbidity, high mortality, major physical disability and poor quality of life. Attainable intensive glycemic control, although necessary, is insufficient to prevent adverse nervous system effects, justifying a therapeutic need to identify new drug targets to treat DN early in its course. Evidence for an important role of low-grade inflammation and of nuclear factor kappa B (NF- $\kappa$ B) activation in the pathogenesis of DN is emerging from both experimental and clinical studies. Salsalate, a nonacetylated prodrug of salicylate, is an FDA approved treatment for osteoarthritis and other rheumatologic conditions. It is a highly effective drug in blocking the inhibitor of  $\kappa$ B kinase (IKK $\beta$ )/NF- $\kappa$ B pathway, with a large margin of safety, and low cost.

### Objectives:

**Primary:** Determine whether a 12-month course of oral salsalate (up to 3 grams daily) will prevent the progression of DN, as measured by intraepidermal nerve fiber density (IENFD) at the proximal thigh and distal leg in subjects with T1DM and mild DN.

**Secondary:** Determine whether a 12 month course of up to 3 grams of salsalate daily will have an effect on:

1. The change from baseline to months in IENFD at the distal thigh;
2. The proportion of subjects with confirmed clinical neuropathy at baseline, and 12 months defined as the combination of:
  - a) Definite clinical neuropathy requiring at least two positive responses among neuropathic symptoms (pain, numbness, paresthesias), sensory signs, and abnormal ankle reflexes (diminished or absent) consistent with a distal symmetrical polyneuropathy and without causal explanation aside from diabetes, as assessed clinically using a standardized neurological examination; and
  - b) NC abnormalities involving  $\geq 2$  nerves among the sural, peroneal, and ulnar nerves.
3. The proportion of subjects with definite small fiber neuropathy, defined as neuropathic symptoms and signs (decreased pinprick or temperature sensation) consistent with small fiber predominant dysfunction, and an abnormality in IENFD (one standard deviation below normal for age/gender/weight) or abnormal cardiovascular autonomic testing.
4. Measures of cardiovascular autonomic neuropathy derived from cardiovascular reflex testing (R-R interval ratio during deep breathing, postural change, and Valsalva) at baseline and 12 months; resting HR will be obtained at baseline and 3 month intervals through 12 months of follow-up.
5. Measures of quality of life as assessed by the NeuroQOL domain and overall scores at

baseline, 6, and 12 months.

6. Autonomic symptoms will be assessed using the Survey of Autonomic Symptoms (SAS).

7. Measures of pain as assessed by the Neuropathy Pain Scale

8. Functional Assessments: BERG Balance Scale; Falls Efficacy Scale, and 8 Foot Get-Up-and-Go assessments.

**Exploratory:** Assessment of expression of pain-related molecules in skin biopsies, including sodium channels, TrkA receptors, neuropeptides, such as substance P and CGRP and TNF $\alpha$ . Serum inflammatory markers TNF $\alpha$ , IL1 $\beta$ , IL6 and CCL2 will also be measured.

**Trial Design:** This is a phase II-III, multi-site randomized, double-blind, placebo-controlled clinical trial to evaluate the effect of salsalate on measures of small fiber neuropathy in 70 subjects with T1DM and mild DN. Subjects will be randomized in a 3:2 fashion to (up to) 3 grams/day salsalate or matched placebo and receive study medication for 12 months. Randomization will be stratified by baseline HbA1c (( $\leq$ 8.0 or  $>$ 8.0%)). Subjects will be evaluated every 3 months for a total of 12 months.

### **Endpoints:**

**Primary outcome:** Change from baseline to month 12 in the intraepidermal nerve fiber density (IENFD) at the distal thigh.

### **Secondary outcomes:**

IENFD at the ankle at baseline and 12 months

#### Electrophysiological measures

- *Nerve Conduction Studies* of the sural, peroneal, and ulnar nerves will be obtained at screening and 12 months
- *Quantitative Sensory Testing*: Cold and vibration thresholds are assessed at screening and 12 months.
- *Measures of CAN* will comprise cardiovascular reflex testing using the DCCT/EDIC protocol (R-R interval ratio during deep breathing, postural change, and Valsalva).

Clinical measures of DN will be assessed at baseline and 12 months and will include:

- a) *DN symptoms* as evaluated by the *Neuropathy Total Symptom Score-6 (NTSS-6)*
- b) *Survey of Autonomic Symptoms (SAS)*
- c) *The DCCT/EDIC Structured Neurological Examination*

Measures of DN- specific pain will include the pain domain part of the *NeuroQOL* and the *Neuropathic Pain Scale* that will be administered at baseline, 6, and 12 months.

Functional scales will be assessed at baseline and 12 months and include:

- a) *The Berg Balance Scale* which measures balance in 14 separate activities of daily living such as going from sitting-to-stand and standing on one leg; the unipedal stance portion that had been shown to be particularly reflective of neuropathy-related mobility loss;
- b) *The 8 Foot Up and Go Test*, a test of functional mobility that assesses the time needed for a subject to arise from sitting position, walk 8 ft and turn 180 degrees around a cone and return sitting;
- c) *The Modified Falls Efficacy Scale* assessing patient's self-reported ability to perform activities of daily living (e.g. get dressed/ undressed, walking, shopping).

Quality of life measures will be administered at baseline, 6, and 12 months and include *the NeuroQOL*, a validated measure of quality of life specific to peripheral neuropathy.

**Exploratory outcomes:** will be assessed at baseline and 12 months and include:

- a) Assessment of expression of *pain-related molecules in distal leg skin biopsies*, including the ion channel TRPV1, TrkA receptors, and neuropeptides, e.g. substance P and CGRP, using our published protocol;
- b) *skin nerve fiber inflammatory markers* including TNF $\alpha$ , IL1 $\beta$ , CD68c, using our published protocol; and
- c) a complex panel of serum inflammatory markers using the Luminex 200 platform (Luminex Corporation, Austin, TX) and Millipore multiplex immunoassay panels (Millipore Corporation, Chicago, IL, which offers customization of 40 different cytokines including TNF $\alpha$ , sTNF receptor, IL1 $\beta$ , IL6, MCP-1, adiponectin, IL8, IL17, m-CSF, sVCAM-1, s-ICAM-1, IL10; and
- d) urine inflammatory markers using the Luminex 200 platform which offers customization for urinary cytokines as outlined above

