**Table 1: Proposed Visit Schedule for TINSAL-T1DN Study**

Visit Number	Visit 1	Visit 2	Visit 3	Visit 4**	Visit 5	Visit 6**	Visit 7
Visit Description	Screening	Baseline	Monitoring	Monitoring	Monitoring/ Outcomes	Monitoring	Monitoring/ Outcomes
Time point	Day -180 to 0	Day 0	Month 1	Month 3	Month 6	Month 9	Month 12
Visit window		NA	± 7 days	± 14 days	± 14 days	± 14 days	± 14 days
Informed Consent	X						
Medical History /Physical Examination†	X	X		X	X	X	X
Laboratory Measures*	X			X	X	X	X
Skin Biopsies (proximal/distal leg)		X					X
Neurological History /Physical Examination†	X						X
Nerve Conduction Studies	X						X
Neuropathy Total Symptom Score	X	X			X		X
Cardiovascular Autonomic Studies		X					X
Resting Heart Rate		X	X	X	X	X	X
Quantitative Sensory Testing	X						X
NeuroQOL		X			X		X
Survey of Autonomic Symptoms		X			X		X
Neuropathy Pain Scale		X			X		X
Functional Assessments							
Berg Balance Scale							
8-foot Get Up and Go Test		X					
Modified Falls Efficacy Scale							X
Medication Dispensing§		X		X	X	X	
Medication Compliance			X	X	X	X	X
Medication Return				X	X	X	X
Adverse Events Monitoring		X	X	X	X	X	X

† Baseline history and examination will include diabetes duration, diabetes complications, diabetes treatment, concurrent medical problems, relevant past surgical history, height, weight, blood pressure and pulse, and foot examination. Follow up visits will include changes in medical or surgical history, weight, blood pressure, pulse and foot examination \* HbA1c, Metabolic Comprehensive Panel, Complete Blood Count with Platelets, TSH, Lipid Profile, Cystatin-C, Uric Acid and Urine Albumin performed at screening visit (unless results for these tests are documented in the medical record as being done in the prior 3 months for all except HbA1c (1 month) and Urine Albumin (6 months). Urine pregnancy test at screening for all women of childbearing potential regardless of contraceptive practiced. HbA1c, Metabolic Comprehensive Panel, CBCP, Cystatin-C, Uric Acid and Urine Albumin will be repeated at 3, 6, 9 and 12 months of follow-up. Lipids will be repeated at 3, 6 and 12 months of follow-up. Luminex inflammatory marker assays on blood and urine performed at screening or baseline, and again at study end.

\*Visit windows for visit 3-7 are based off when the patient starts the study medication following visit 2 due to the shipping of the medication from Belmar Pharmacy directly to the participant.

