## 6.2. Baseline

### Visit 2: Baseline (Day 0).

The key activities of the baseline visit are to obtain the initial skin biopsies and to initiate treatment with either Salsalate or placebo. Cardiovascular autonomic neuropathy (CAN) assessment, as well as quality of life and symptom questionnaires, and a short battery of functional assessments, will also be performed at the baseline visit. Two skin biopsies are obtained; one at the proximal thigh, and one at the distal leg. These will be done on the subjects' dominant side unless contraindicated (e.g., presence of a cast).

Upon satisfactory completion of all eligibility and baseline assessments, including the skin biopsy, a 3 month + 14-day supply of Salsalate or placebo will be provided, and written instructions for use of the medication reviewed with and provided to the subject. Subjects will be instructed to take one tablet with breakfast for the first four days beginning with the first breakfast after receipt of the study medication. The study medication dose will be increased slowly to the maximum tolerated dose (2 tablets, 3 times daily) using the following schedule: Beginning on day 5, take 1 tablet with breakfast and 1 tablet with lunch. Beginning on day 9, take 1 tablet at breakfast, 1 tablet at lunch, 1 tablet at dinner. Beginning on day 23, take 2 tablets at breakfast, 1 tablet at lunch, 1 tablet at dinner. Beginning on day 27 take 2 tablets at breakfast, 2 tablets at lunch, 1 tablet at dinner. The maximum dose of study medication, 2 tablets at breakfast, 2 tablets at lunch, and 2 tablets at dinner, may be started no sooner than the 31st day from receiving the first supply of study medication.

Subjects are to be reminded to return any unused study medication at their next visit.

Study staff will contact the subject within one week of the baseline visit to assess medication compliance and tolerance and to inquire as to the status of the biopsy sites.

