#### Visit 5: Safety Monitoring and Drug Dispensing (Month 6).

At this visit, the study staff will measure the weight, blood pressure and resting heart rate, and will ask the subject about any changes in health status or physical symptoms. Laboratory assessments (HbA1c, METCOMP, CBCP, cystatin-C, lipids, uric acid and urine albumin) will be obtained. Urine pregnancy testing may be performed at the discretion of the investigator for all women of childbearing potential. The study staff will collect any unused study medication, and will dispense a 3 month + 14-day supply of study medication. The number of unused salsalate tablets will be recorded in the source document and unused medication secured until returned for final drug disposition. The subjects will be asked to complete quality of life and neuropathy symptom surveys.

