#### Analyses of Secondary Outcomes:

Due to multiple tests, formal statistical testing won't be performed; p-values will be reported to allow the reader to assess the result. For analysis of repeated measures of continuous data (change from screening/baseline to 12 months in NC studies, quantitative sensory testing, CAN measures, Neuropathy Symptoms, Pain, and NeuroQOL domain scores), a longitudinal approach will be employed. Specifically, each outcome will be analyzed using a mixed effect model for repeated measures with the treatment group and baseline HbA1c ( $\leq 8.0$  or  $> 8.0\%$ ) as fixed covariates. Under the model, time of assessment will be a continuous variable and the outcome will be modeled as a linear function of time. Appropriate non-linear parametric or non-parametric tests may be applied if assumptions of the model are not satisfied.

Logistic regression will be used to compare the proportion of subjects who have confirmed clinical neuropathy with NC and those who had normal NC and therefore required an assessment of IENFD for trial entry, between the salsalate and placebo groups, with covariates for treatment group, and baseline HbA1c ( $\leq 8.0$  or  $> 8.0\%$ ). The components of this composite endpoint will also be assessed. Rank-transformation analysis of covariance will be used on each of the NC values, and an overall treatment group differences in the multiple NC values will be assessed using the nonparametric Wei-Lachin rank test of stochastic order. The impact of additional covariates on the relationship between IENFD and confirmed clinical neuropathy and treatment will be explored by adding age, sex, height, weight, BMI, cigarette smoking, cardiovascular risk factors and concomitant medications into the models described above. A forward stepwise selection procedure will be used, with  $p < 0.10$  used to retain covariates. Interaction terms between treatment groups and select covariates will be investigated. In addition, we will adjust for the effect of changes in glucose on outcomes during the course of treatment by including HbA1c as a time-varying covariate in models.

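### NTSS-6: the symptom model has no pre-treatment score as covariate and no rule for the screening score; adding the Visit 2 score as a covariate improves precision with data already collected

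*Combined protocol and SAP*

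**What the plan says.** - **Outcome lists** (Synopsis, secondary outcomes; repeated in Section 2). The NTSS-6, the Survey of Autonomic Symptoms (SAS) and the structured neurological examination share one introductory line: "Clinical measures of DN will be assessed at baseline and 12 months and will include". The same lists give pain and quality of life a month-6 assessment, but not these three.
- **Table 1.** The row "Neuropathy Total Symptom Score" is marked at Visit 1 (screening), Visit 2 (baseline), Visit 5 (month 6) and Visit 7 (month 12). The SAS row is marked at Visits 2, 5 and 7. Screening may fall up to 180 days before Visit 2.
- **Sections 6.2 and 6.3.** Visit 2 includes autonomic testing "as well as quality of life and symptom questionnaires". At Visit 5, "The subjects will be asked to complete quality of life and neuropathy symptom surveys".
- **Section 10.2, secondary outcomes.** Symptoms belong to a list described as "change from screening/baseline to 12 months in NC studies" and other measures, which ends "Neuropathy Symptoms, Pain, and NeuroQOL domain scores), a longitudinal approach will be employed". The model is "a mixed effect model for repeated measures with the treatment group and baseline HbA1c" stratum as covariates, with time continuous and its effect linear. No pre-treatment score is listed as a covariate, and no rule covers an outcome scored twice before treatment. Secondary outcomes are not formally tested, but p-values are to be reported.

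**The concern.** NTSS-6 is the only listed secondary scale that Table 1 schedules twice before treatment, and the plan does not say how either score enters the model. Two things follow.

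First, a model that treats the Visit 2 score as one more response on a line, or subtracts it to form a change, usually gives a less precise treatment comparison than one that adjusts for it. With about 50 completers planned, that precision is worth having, and it costs nothing to collect.

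Second, the screening score could be ignored, used as the reference, or placed on the time axis. The last of these would dilute the estimated effect. The choice is not purely descriptive: Section 10.1 makes one route to trial success depend on a secondary endpoint trending the same way as the primary. A symptom trend that can be computed in several ways should be fixed before unblinding.

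**Working it through.** **Plan's own figure.** The documents give no power, SD or correlation for NTSS-6. The only power figure, 81% in Section 10.1, is for thigh nerve fiber density. A two-sample t-test with 25 per group, difference 1.65 and SD 2.0 gives 81.5%, so it reproduces, but it has no bearing here. All correlations below are assumptions. Variances are per unit of outcome variance.

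**Step 1: what the linear model estimates.** With times 0, 6 and 12, deviations from the mean time are -6, 0 and 6. The least-squares slope is (6·y12 - 6·y0)/72 = (y12 - y0)/12. Twelve times the slope is simply the change from Visit 2 to month 12, and month 6 carries no weight. This holds for an unweighted or equal-correlation fit with complete data.

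**Step 2: change or slope versus Visit 2 as covariate.** Let any two scores in a subject correlate r. The change has variance 2(1 - r). Month 12 adjusted for Visit 2 has residual variance 1 - r². The reduction is 1 - (1 - r²)/[2(1 - r)] = (1 - r)/2.

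| r (assumed) | Change or slope | Visit 2 as covariate | Reduction |
|---|---|---|---|
| 0.5 | 1.00 | 0.75 | 25% |
| 0.6 | 0.80 | 0.64 | 20% |
| 0.7 | 0.60 | 0.51 | 15% |

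The standard error falls by 1 - √0.75 = 13% at r = 0.5 and by 1 - √0.85 = 8% at r = 0.7.

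**Step 3: what the screening score adds.** Under equal correlation, replacing Visit 2 by the mean of the two scores takes the residual variance from 1 - r² to 1 - 2r²/(1 + r): 0.75 to 0.667 at r = 0.5 (11%) and 0.51 to 0.424 at r = 0.7 (17%). Equal correlation is doubtful when the scores may be six months apart. Let correlation at lag t months be q·exp(-kt), with q = 0.8 to 0.9, a 12-month correlation of 0.5 to 0.7, and screening 1 or 6 months before Visit 2. Relative to Visit 2 alone:

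- both scores as separate covariates: 0.3% to 10% less variance;
- their simple mean as covariate: from 3% more to 10% less.

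Worst case in that range: q = 0.9, 12-month correlation 0.5, gap 6 months. Then k = ln(0.9/0.5)/12 = 0.049, screening correlates 0.671 with Visit 2 and 0.373 with month 12. Separate covariates give 1 - (0.25 + 0.139 - 2·0.5·0.373·0.671)/(1 - 0.45) = 0.747 against 0.75. The mean gives 1 - 0.436²/0.835 = 0.772, which is worse than Visit 2 alone.

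**Step 4: screening as a time point.** Suppose the true difference between arms is 0 up to Visit 2 and grows linearly to 1 at month 12. Fit an unweighted line to the differences at -L, 0, 6 and 12. For L = 6 the mean time is 3, the sum of squares is 180 and the cross-product is 3·0.5 + 9·1 = 10.5, so 12 × slope = 12 × 10.5/180 = 0.70. For L = 3 it is 12 × 9.375/132.75 = 0.85. For L = 1 it is 12 × 8.625/108.75 = 0.95.

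**Step 5: within-arm change.** If entry selects on the screening score and raises it by d, Visit 2 and month 12 are both expected at r·d. Spurious change is then 0 from Visit 2, -(1 - r)d from screening, and r·d - (1 + r)d/2 = -(1 - r)d/2 from the mean.

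**The case against.** The strongest reply is that the plan already works. Symptoms are in a longitudinal model, so month 6 can enter it. The screening/baseline wording covers a mixed list and most naturally means whichever visit applies to each outcome, which for NTSS-6 is Visit 2. Nothing says that screening goes on the time axis. Using Visit 2 as baseline is conventional and valid. Section 6.1 does not name NTSS-6 among the Visit 1 procedures, so the screening score rests on one cell of Table 1. Section 10 defers detailed methods to an analysis plan to be finalized before unblinding. The outcome is secondary and not formally tested.

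Much of this stands. A reader might infer that the month-6 and screening scores are discarded. The documents do not support that: their role is undefined rather than nil. A reader might also infer that averaging the two pre-treatment scores gives an 11% to 17% gain for nothing. That rests on equal correlation over a gap of up to 180 days, and Step 3 shows that the mean can lose precision. Nor does averaging reduce regression to the mean relative to Visit 2 alone; Step 5 shows the reverse. The selection premise is itself thin, because Section 4.1 sets no NTSS-6 threshold.

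Two things do not fall. The natural reading is not secure, since the neurological examination sits under the same baseline-and-12-months line although Table 1 schedules it at screening and month 12. And even with Visit 2 as the reference, no pre-treatment score is listed as a covariate. If the intended model forces the arms to share a common mean at Visit 2, it would already have much of the gain, but the plan does not say so.

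**Conclusion.** The point holds as a modest, cost-free improvement to one secondary analysis and as a gap in the specification. Against a change or 0-6-12 slope analysis, the Visit 2 score as covariate cuts variance by about 15% to 25% at assumed correlations of 0.7 to 0.5. The screening score as a separate second covariate adds 0.3% to 10% if correlation decays as in Step 3. Excluding screening as a response time avoids an attenuation to 95%, 85% or 70% for gaps of 1, 3 or 6 months; those figures assume an unweighted fit and linear growth of the effect from Visit 2. The mismatch between the outcome lists and Table 1 is editorial on its own. The primary outcome and the sample size are not affected.

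**What to change.** 1. **Section 10.2.** State that NTSS-6 is analyzed with months 6 and 12 as the responses and the Visit 2 score as a baseline covariate, alongside treatment and HbA1c stratum, and that the treatment effect is the difference at month 12. With two response times, a linear time term with a treatment-by-time interaction already allows a separate difference at each visit.
2. Optionally add the screening score as a second, separate covariate. Do not enter it as a response time, and do not replace Visit 2 by the mean of the two scores.
3. Use Visit 2 as the reference for reported within-arm change.
4. **Synopsis and Section 2.** Align the timing with Table 1: NTSS-6 at screening, baseline, 6 and 12 months; SAS at baseline, 6 and 12 months.
5. If Table 1 is right that NTSS-6 is done at Visit 1, name it in Section 6.1.

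The cost is wording, settled before the blind is broken, and one degree of freedom per covariate. No new data are needed.

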#### **Trial Treatments:**

Oral administration of salsalate up to 3 grams/daily for 12 months, or

Oral administration of matched placebo daily for 12 months.

#### **Statistical Methods:**

We reported that the average IEFND in the distal leg in T1DM subjects (mean disease duration of 27 years) was 2.2 fibers/mm. We assume that the targeted diabetic subjects have the average IENFD for ages 20-29 shown by published normatives at the start of their disease, and the decline due to diabetes is 10 fibers/mm or an average of 0.25 fibers/mm/year. If the decline is more rapid as neuropathy progresses, then the average decline in IEFND may be as high as 0.5 fibers/mm/year. Based on our assumption about the mechanism by which salsalate will influence IEFND (reduction of inflammation), and published effect of other interventions, we believe that an increase of 1.65 fibers/mm (0.25 + 1.4 = 1.65) in fiber density is possible with treatment with salsalate. The standard deviation

of the change is approximately 2 fibers/mm. With 25 subjects per group there will be 81% power to reject the null hypothesis of no difference between groups using a two-tailed t-test at a 5% level of significance. No formal interim analysis for stopping for efficacy benefit or futility is planned, given the projected duration of follow-up required for the assessment of the primary endpoint. Rather, safety will be assessed periodically and reviewed by a Data and Safety Monitoring Board.

A general linear model will be fitted to the change in IENFD score with factors for treatment group, baseline HbA1c ( $\leq 8.0$  or  $> 8.0\%$ ), and baseline IEFND as fixed covariates. If the distributional assumptions are not met, transformations of IENFD or the use of nonparametric methods will be employed. Sensitivity analyses will be performed to assess how subjects who withdrew may affect conclusions of the analysis. An intent-to-treat analysis set (including subjects who are randomized, treated and have a baseline IENFD) will be used to assess treatment effects with multiple imputation methods employed to impute outcomes for subjects with missing post-baseline data.

